#### Cost-effectiveness

Category	Measurement instrument	Time
Medication	Data from medical records	12 months

Scheduled and unscheduled healthcare utilisation	Data from medical records	12 months
Referrals	Data from medical records	12 months
Costs	Data from medical records	12 months
	Medical consumption questionnaire	Baseline, 3, 6, 9, 12 months
	EQ-5D-5L	Baseline, 6, 12 months

#### 4.4 Withdrawal of individual subjects

Subjects can leave the study at any time for any reason if they wish to do so without any consequences.

#### 4.5 Replacement of individual subjects after withdrawal

Subjects will not be replaced after withdrawal

#### 4.6 Follow-up of subjects withdrawn from treatment

For intention-to-treat analyses all available data from patients will be used. Patients who withdraw will be asked to fill the questionnaire for the measurement of the primary outcomes at 12 months.

#### 4.7 Premature termination of the study

The study will be terminated in its current design as recruitment of the necessary number of cluster fails.

### 5. SAFETY REPORTING

As all patients will at least receive care similar to usual care, we do not expect any safety issues for participants.

### 6. STATISTICAL ANALYSIS

Data analysis will be performed according to the intention-to-treat principle. Data from patients who discontinued follow-up will be included in the analysis up to the point of dropout. Descriptive analyses will be performed to describe the patient characteristics. Mean and standard deviation (std) or median and interquartile range for continuous characteristics and number and percentages for categorical characteristics will be determined. The relationship between treatment and outcome measures measured at 6 and 12 month follow up will be analysed with mixed three level linear or logistic regression, taking into account that the times of measurement (after 6 and 12 months) are clustered within patients, and patients within general practices. We will perform a

model with a random intercept and all other variables fixed. To test the effect of the intervention a model with time, group (intervention or control) and the interaction between time and group will be performed. Covariates included in the analyses will be age, sex, smoking status, education level, and social support. A value of  $p < 0.05$  will be considered statistically significant for all analyses, based on two-sided testing. Analyses will be performed using the Statistical Package for Social Sciences (SPSS, IBM Corp., Armonk, NY) version 25.

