**Intervention:** a GDM programme including person-centered and holistic care. This programme will replace the SDM programmes for DM2, COPD and CVD that are currently used in the participating primary care cooperatives.

**Main study parameters/endpoints:** effectiveness will be evaluated by Quadruple Aim outcomes at baseline, at 6 months, and at 12 months follow-up by comparing changes in the intervention group with the comparator group. Patient experiences will be measured with the P3CEQ questionnaire. Population health will be measured with the PROMIS Global-10 questionnaire. Self-management will be measured with the Patient Activation Measure (PAM) score. Healthcare professional experiences will be measured with the MASGZ and the COPILOT questionnaire. Data for calculating costs and conducting a cost-effectiveness analyses will be measured by the Medical Consumption questionnaire and the EQ-5D questionnaire and by process outcomes such as the number and type of consultations and referrals, and duration of consultations from the Electronical Medical Files. At 12 months, a purposive sample of patients and professionals will participate in focus group interviews to collect information on experiences and facilitators and barriers for further implementation. Also, the competences needed by the healthcare professionals to provide personalised and integrated chronic care will be explored.

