## **4. METHODS**

### **4.1 Study parameters/endpoints**

Outcome measurement will be based on the quadruple aim framework.[16] To measure population health we will assess quality of life, self-management, and disease-specific physiological factors. Our composite primary outcome will be health-related quality of life *and* patient experience, measured with the PROMIS Global 10 and P3CEQ, as described in paragraph 2.4. Secondary outcomes will be: self-management, measured with the Dutch short version of the patient activation measure (PAM-13).[17] Measurement of disease-specific physiological factors will take place as part of routine care in both study groups and include blood pressure, body mass index (BMI), cholesterol, blood glucose levels and lung function parameters, if applicable. All outcomes will be measured at baseline, 6 months, and 12 months follow-up. Physiological factors will be recorded in the electronic medical records as part of routine care and will be extracted from 3 months before baseline until 12 months follow-up. Also, healthcare utilisation and prescription data will be extracted from the electronic medical records at the end of follow-up. Health care provider experiences will be measured with an appropriate self-reported experience measure.

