#### 4.2 Randomisation, blinding and treatment allocation

The unit of randomisation will be the general practice (cluster). Practices will be randomised to intervention group (10 clusters) or comparator (5 clusters) in a 2:1 ratio. Five additional clusters will be randomised to the control group by a 2:1 ratio randomisation procedure in the parallel cluster RCT named EMBOSS in which the GDM programme will be adjusted to the needs of patients with low socioeconomic status (SES). In the EMBOSS cluster RCT the adjusted intervention will be provided to patients with low SES and at 12 months follow-up the effects will be compared to patients with low SES who have received care as usual. Figure 2 illustrates the combined randomisation procedure of both the OPTIMA FORMA and the EMBOSS cluster RCT.

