**Figure 2. Randomisation procedures in the OPTIMA FORMA and EMBOSS cluster RCTs**

After practices have been recruited, the practices will be randomised to the intervention or the usual care group. To avoid an imbalance between the randomised groups stratification will take place according to (i) the primary care cooperative, and (ii) the socioeconomic status of the practice population. Because of the nature of the intervention, it will not be possible to mask intervention allocation from the GPs or the patients. The research nurses who will collect the outcome data and the researchers who will perform the analyses will be blinded to treatment allocation.

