### **6.1 Primary study parameter(s)**

Our primary outcome is a dichotomous composite score ( yes / no MCID improvement in health-related quality of life or quality of healthcare), which is based on the scores of PROMIS dimensions (GPH, GPM) and the P3CEQ-score.

To test the effect of the intervention over time, we use a three level multilevel logistic model. A model with time , group (intervention or control) and the interaction between time and group will be performed. With this model we can test the effect of the intervention during the entire study period and the intervention effects at 6 months and at 12 months.

In a mixed model both fixed and random effects can be analyzed. We perform a model with random effect for practice and patients. All other variables will be held fixed. Covariates included in the analyses will be age, sex, smoking status, education level, and social support.

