### **6.2 Secondary study parameter(s)**

The relationship between treatment and secondary outcome measures measured at 6 and 12 month follow up will be analysed with mixed three level linear or logistic regression, taking into account that the times of measurement (after 6 and 12 months) are clustered within patients, and patients within general practices. A model with time, group (intervention or control) and the interaction between time and group will be performed. Covariates included in the analyses will be age, sex, smoking status, education level, and social support

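### The continuous patient-reported secondary outcomes are not adjusted for their own baseline values, follow-up value or change is left open, and the test of group has no named small-sample reference

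*Combined protocol and SAP*

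**What the plan says.** **Covariates.** Section 6 lists them as "Covariates included in the analyses will be age, sex, smoking status, education level, and social support", and 6.1 and 6.2 repeat the list. It holds no baseline score of a continuous outcome and no stratification factor.

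**Occasions.** Under 6.2, "secondary outcome measures measured at 6 and 12 month follow up will be analysed with mixed three level linear or logistic regression". Baseline is therefore not an outcome occasion either.

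**Baseline data.** Section 4.1 states: "All outcomes will be measured at baseline, 6 months, and 12 months follow-up". The tables in 4.3 list PROMIS, P3CEQ, PAM and EQ-5D at baseline. Physiological values come from routine records and "will be extracted from 3 months before baseline until 12 months follow-up".

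**What is compared.** The Summary says effectiveness is judged "by comparing changes in the intervention group with the comparator group". Section 6.2 does not say whether a continuous outcome enters as a follow-up value or as a change.

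**Strata.** Section 4.2 (under Figure 2) says "stratification will take place according to (i) the primary care cooperative, and (ii) the socioeconomic status of the practice population". The number of socioeconomic levels is not given.

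**Clusters and test.** Section 4.2 randomises 10 and 5 practices, and adds: "Five additional clusters will be randomised to the control group by a 2:1 ratio randomisation procedure in the parallel cluster RCT named EMBOSS". On the primary, 6.1 says "We perform a model with random effect for practice and patients". The plan fixes two-sided p < 0.05 in SPSS 25 and names no degrees-of-freedom method.

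**The concern.** For a continuous score, the patient's own starting value is usually the strongest predictor of the later value. Leaving it out of a model for follow-up values gives away precision that the trial has already paid for. Modelling changes without it recovers only part of that precision.

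The ambiguity matters as well. Two analysts could follow 6.2 faithfully, one modelling follow-up values and the other changes, and report different estimates and p-values. With every practice-level contrast resting on 15 to 20 practices, such choices can decide significance, and so can the reference distribution for the group effect.

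**Working it through.** **1. Reproducing the planned size, to fix the inputs.** From section 2.4: 35% against 20%, two-sided 5%, 80% power, ICC 0.03, 40 patients per practice, 20% loss. Equal arms need 138 patients each, 276 in total. Completers per practice: 40 × 0.8 = 32. Design effect: 1 + 31 × 0.03 = 1.93. Then 276 × 1.93 = 532.7; 532.7 / 0.8 = 665.8; 665.8 / 40 = 16.65, rounded up to 17 practices, or 680 patients. This is the plan's figure, so I use m = 32 and ICC = 0.03. Section 2.4 gives that ICC for the composite; carrying it over to the continuous scores is an assumption.

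**2. Continuous secondary outcomes.** Let r be the baseline to follow-up correlation (not in the documents), with adjustment acting between patients within practices only. In units of the outcome variance, a practice mean has variance:

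- follow-up value, no baseline: 0.03 + 0.97/32 = 0.03 + 0.0303 = 0.0603
- change, no baseline: 0.03 + 0.0303 × 2(1 − r), with the practice component held at 0.03
- own baseline as covariate: 0.03 + 0.0303 × (1 − r²)

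| r | follow-up value | change | adjusted | cut vs follow-up value | cut vs change |
|---|---|---|---|---|---|
| 0.6 | 0.0603 | 0.0543 | 0.0494 | 18.1% | 8.9% |
| 0.7 | 0.0603 | 0.0482 | 0.0455 | 24.6% | 5.7% |

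Sensitivity of the cut against follow-up values:

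- r = 0.3: 4.5%; r = 0.5: 12.6%; r = 0.8: 32.2% (ICC 0.03).
- ICC 0.05: 13–18%; ICC 0.01: 27–37% (r 0.6–0.7).
- If the five listed covariates already explain 5–15% of patient-level variance, the added cut is about 11–17% at r = 0.6 and 18–24% at r = 0.7.
- If the practice component shrinks equally, the cut is r², that is 36–49% at r 0.6–0.7.

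**3. Composite primary.** It is already built from change since baseline. The patient-level share of variance is 0.0303 / 0.0603 = 0.503, so baseline scores explaining a share R² of the outcome cut the variance by about 0.503 × R² (linear approximation). Simulating three correlated scores (0.6 between the PROMIS scales, 0.2 with P3CEQ) at retest correlations 0.6–0.8 gives R² of about 0.05–0.11, a cut of about 3–6%. Those assumptions imply a responder rate of 34–35% with no treatment effect, against the planned 20%. At retest 0.90–0.95 the rate is about 26–14%, R² is 0.023–0.008 and the cut is 1.2–0.4%.

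**4. Reference for the group effect.** If a normal critical value of 1.96 were used where a t distribution on practices − 2 applies, the true two-sided error would be 7.2% on 13 df (15 practices), 6.9% on 15 df (17) and 6.6% on 18 df (20).

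**5. Strata.** Three cooperatives and two assumed socioeconomic levels cost 2 + 1 = 3 df. At 15 practices, df falls from 13 to 10 and the critical value rises from 2.160 to 2.228. Break-even needs a variance reduction of 1 − (2.160/2.228)² = 6.0% if the strata are orthogonal to group, and more if they are not. With a normal reference on 10 df the error would be 7.8%.

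**The case against.** **The size is not in the plan.** Correct: 18–25% rests on an assumed correlation and on follow-up values being modelled. The only relevant statement in the documents points to changes, and on that reading baseline data are partly used and the gain is 6–9%. Nor is 25% a ceiling, as the sensitivity figures show. The omission and the ambiguity do not depend on r.

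**Not every outcome has a baseline.** This stands. Health care use from practice records is extracted at the end of follow-up (4.1), with no baseline period stated. Physiological values rely on a three-month window before baseline, while 3.2 puts usual-care visits at one to four a year, so some patients may have none. A blanket rule could drop patients.

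**Strata terms may not pay.** This also stands. How much the strata explain is unknown, and with 15 practices they can cost more than they return.

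**Stronger readings the documents do not support.**

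- A reader might infer that the primary result is biased. Under randomisation, chance baseline imbalance adds variance, not bias, and the composite is already scored from change.
- A reader might infer that the type I error is inflated. The plan names no normal reference, so the error rate is open rather than shown to be wrong.
- A reader might infer that leaving out the strata invalidates the test. With a t reference, omitting prognostic strata tends to make it conservative.
- A reader might want the primary analysis replaced. The small gain does not justify that, and in a logistic model adding baseline scores also changes the conditional odds ratio being estimated.

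**Conclusion.** The point holds for the continuous patient-reported secondary outcomes. Their baseline values are collected and unused as covariates, and 6.2 leaves open what is being modelled. Own-baseline adjustment would cut treatment-effect variance by about 18–25% against follow-up values, or 6–9% against changes, at an assumed correlation of 0.6–0.7, ICC 0.03 and 32 completers per practice. For correlations of 0.3–0.8, the range against follow-up values is about 5–32%. The gain is somewhat less if the listed covariates already carry part of it.

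For the primary, the gain is a few percent at most, and about 1% or less under assumptions nearer the planned control rate. The unnamed reference distribution is a gap worth closing with or without strata terms. This is an improvement the plan should make, not a flaw that undermines the trial.

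**What to change.** 1. In 6.2, add each continuous outcome's own baseline value as a covariate wherever a baseline measurement exists, and state that the follow-up value is the outcome. Follow-up and change analyses then give the same group effect, which settles the ambiguity and matches the Summary. Name the outcomes that have no baseline.
2. Keep patients with a missing baseline, for example by simple imputation of the baseline value, and state the rule.
3. In 6, 6.1 and 6.2, base the test of group on a named small-sample reference with practice-level degrees of freedom, not a normal reference.
4. Optionally add cooperative and practice socioeconomic stratum as fixed effects, only together with item 3, and define the socioeconomic levels. If they are left out, say why.

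Items 1 to 3 are changes of wording that need no new data collection. Item 1 costs no practice-level degrees of freedom. Item 3 gives wider intervals than a normal reference would. Item 4 costs about 3 of 13 practice-level df with 15 practices and two socioeconomic levels. All should be fixed before allocation is unblinded to the analysts.

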## 2. STUDY DESIGN

We will perform a cluster randomized controlled trial with a follow-up time of 12 months.

The three participating primary care cooperatives, i.e. Nijmegen, Arnhem, and Doetinchem, will recruit 15 general practices (clusters) who will be randomized using a 2:1 ratio in two study groups:

1. The intervention group: the GDM programme including a person-centered, integrated, and holistic approach
2. The control group: care as usual according the current SDM programmes

All practices will receive instructions from the research team on the procedures of the evaluation study. Participating practices will then start recruiting patients from a random sample of eligible patients, i.e. patients with DM2, COPD, or CVD who are currently receiving SDM. After written informed consent, information will be collected through questionnaires at baseline, 6 months and 12 months, and by interviews and data collection from electronic medical records. Information will also be collected from the participating healthcare providers through questionnaires and interviews.

In the two months prior to the start of the intervention, all practices in the intervention group will be trained in providing GDM by their own primary care cooperative. During follow-up two to three intervention meetings will take place including peer coaching and case study discussions.

Practices who are allocated to the usual care group will not receive any training, but will continue with their SDM programmes.

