Because we value each aim (population health and patient experience) as equally important, we are using a composite primary outcome, which consist of the percentage of patients who have a clinically relevant improvement of at least the minimal clinically important difference (MCID), defined as  $0.5 \times \text{SD}$  of the baseline mean, in either the PROMIS GMH score OR the PROMIS GPH score OR the P3CEQ-score AND who experience no decrease of at least the MCID in either the PROMIS GMH score OR the PROMIS GPH score OR the P3CEQ-score.

In our recent pilot study [unpublished] we followed 98 patients who received our intervention for six months. Of the 79 patients who completed all questionnaires, we found that in 30.4% of the patients the requirements for a positive score on the composite primary outcome were met. Loss to follow-up was 20%. Based on these results and the longer duration of intervention in the evaluation study (12 months vs 6 months), we hypothesised that in the evaluation study 35% of the intervention patients compared to 20% of the usual care patients will improve more than  $0.5 \times$  the expected SD of baseline mean on one of the scores at 12 months, and show no decrease of the MCID on the other scores. We estimate that we need a total sample size of 680 patients (17 practices with an average of 40 patients per practice) to detect a difference of 15% between the control and intervention group, taken into account an alpha level of 5%, a power of 80%, an intra-class correlation coefficient (ICC) of 0.03 [15], and a loss to follow-up of 20%.

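### The plan names no estimator or small-sample reference for testing a practice-level effect on 15 to 20 practices; with a large-sample reference the nominal 5% error would be about 5.5–9%

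*Combined protocol and SAP*

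**What the plan says.** Section 4.2 makes the general practice the unit of randomisation: "Practices will be randomised to intervention group (10 clusters) or comparator (5 clusters) in a 2:1 ratio". Section 2 gives the same total of 15. Section 4.2 also describes five further control practices randomised within the parallel EMBOSS trial, which would make 10 against 10 if they are pooled. Section 2.4 sizes the trial at "680 patients (17 practices with an average of 40 patients per practice", "taken into account an alpha level of 5%, a power of 80%, an intra-class correlation coefficient (ICC) of 0.03" and 20% loss to follow-up, for "35% of the intervention patients compared to 20% of the usual care patients".

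Section 6.1 analyses the composite with a three-level logistic model containing time, group and their interaction. On the random part it says only: "We perform a model with random effect for practice and patients". It is to yield an effect over the whole period and effects at 6 and at 12 months. Section 6 adds that p<0.05 "will be considered statistically significant for all analyses, based on two-sided testing", and names SPSS version 25.

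None of sections 6, 6.1 and 6.2 names an estimator (ML, REML or pseudo-likelihood), a degrees-of-freedom method, a t or permutation reference, or a practice-level analysis.

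**The concern.** Every patient in a practice has the same allocation, so the precision of the group effect depends on the between-practice variance. That variance is estimated from 15 to 20 practices. A normal reference (1.96) treats it as known, and ML also tends to estimate it too low. Both make p-values too small and intervals too narrow, and recruiting more patients per practice does not remove the problem.

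Two things are at stake. The nominal 5% is not secured for the between-practice group effects. And because the method is left open, the reference distribution could be chosen once results are known, when that choice may decide on which side of 0.05 the primary p-value falls.

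**Working it through.** **Inputs from the documents.** Rates of 35% and 20%, ICC 0.03, two-sided alpha 5%, power 80%, 40 patients per practice and 20% loss (section 2.4), so 40 × 0.8 = 32 analysed per practice. Layouts: 10:5 (sections 2 and 4.2), 17 practices (section 2.4, taken as 9:8), and 10:10 if the EMBOSS controls are pooled (section 4.2).

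**The plan's own figure.** Two proportions with normal quantiles and 1:1 allocation need 138 per arm, 276 in total. The design effect is 1 + (32 − 1) × 0.03 = 1.93. Then 276 × 1.93 / 0.8 = 666, or 16.6 practices of 40, rounded up to 17 × 40 = 680. The figure is reproduced, and it contains no allowance for few clusters. At 2:1 allocation the same formula gives 767.

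**Analytic check.** With J practices and two practice-level parameters (intercept and group), df = J − 2. The last column shrinks the variance by (J − 2)/J to mimic ML.

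| Practices | df | t critical value | Ratio to 1.96 | P(\|t\| > 1.96) | With ML shrinkage |
|---|---|---|---|---|---|
| 15 | 13 | 2.16 | 1.10 | 7.2% | 9.1% |
| 17 | 15 | 2.13 | 1.09 | 6.9% | 8.5% |
| 20 | 18 | 2.10 | 1.07 | 6.6% | 7.9% |

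The ratio column is where the 7–10% for interval width comes from.

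**Simulation of the 12-month effect.** 4,000 null trials per setting, 32 patients per practice on average, and a two-level logistic model. Assumptions not in the documents: a null rate of 20% or 30%; ICC 0.03 read on the proportion scale (logit variance 0.03 / (0.2 × 0.8) = 0.1875 at 20%) or on the latent scale (0.10); and practice-size CV 0 or 0.4. The CV 0.4 runs use the 20% rate and the proportion scale.

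| Layout | ML, 1.96, equal sizes | ML, 1.96, CV 0.4 | REML-type, 1.96, equal sizes | REML-type, 1.96, CV 0.4 |
|---|---|---|---|---|
| 10:5 | 7.0–7.8% | 9.1% | 5.7–6.2% | 7.4% |
| 9:8 | 6.9–7.6% | 8.1% | 5.9–6.4% | 6.4% |
| 10:10 | 6.5–7.5% | 7.3% | 5.4–6.0% | 6.2% |

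With t on practices minus 2 df, the same fits reject in 4.3–6.0% (ML) and 3.5–4.9% (REML-type). A separate null simulation at ICC 0.03 gave 7.5% (10:5) and 7.6% (10:10) for ML with z, 6.1% for REML-type with z, and 3.9–5.5% with t.

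**Simulation of the three-level model.** 6 and 12 months, random practice and patient effects, ML with 1.96, patient variance assumed to be 2.0, about 2,500–2,700 null trials per layout.

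| Contrast | 10:5 | 10:10 |
|---|---|---|
| 12-month group effect | 7.1% | 6.7% |
| Whole-period group effect | 8.4% | 7.6% |
| Time-by-group interaction | 5.2% | 5.1% |

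The 6-month effect was not tabulated. The two occasions are exchangeable under this null, so the 12-month rate applies. Monte Carlo standard errors are about 0.4–0.6 points throughout.

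**Power under 35% against 20%.** Variance = [0.35 × 0.65 / (32 × intervention practices) + 0.20 × 0.80 / (32 × control practices)] × 1.93. At 10:5 the standard error is 0.0575 and 0.15 / 0.0575 = 2.61.

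| Layout | Formula, z | Formula, t | Simulated, z | Simulated, t |
|---|---|---|---|---|
| 10:5 | 74% | 67.5% | 76% | 70% |
| 9:8 | 82% | 76.5% | 84% | 80% |
| 10:10 | 87% | 83.5% | 88% | 85% |

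**The case against.** The strongest reply is that the plan is silent rather than wrong. It nowhere commits to a normal reference. If the analyst picks practice-based degrees of freedom, most of the excess disappears, and REML-type fitting alone brings it to about 5.5–6.5% with equal practice sizes. This stands as a limit on the size of the problem. It does not remove the point, because nothing in the plan requires either choice and a large-sample reference exceeded 5% under both estimators in every layout tried.

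Four stronger readings are tempting, and the documents do not support them:

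- *That the primary test runs at 7–9%.* This needs ML and a normal reference, and the plan states neither. The 9% also needs unequal practice sizes, and the documents give no CV.
- *That the practice variance rests on five control practices.* The model has one common practice intercept, so all 15 to 20 practices inform its variance. Five is the size of the control arm.
- *That the inflation holds whatever covariates or strata are fitted, and for every secondary outcome.* The simulations contained no covariates or stratification factors, and no linear model was run.
- *That every time-related contrast needs practice-based degrees of freedom.* The interaction is already near 5%. Holding it to 2.16 would cut its error to about 3%, since P(|Z| > 2.16) = 3.1%.

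**Conclusion.** The point holds in a limited form. For the between-practice group effects (whole period, 6 months, 12 months), a large-sample reference would give a type I error of about 5.5–9% instead of 5%. At ICC 0.03 with equal practice sizes it is about 7–8% under ML and 5.5–6.5% under REML-type fitting. With an assumed CV of 0.4 the highest values, at 10:5, are about 9% and 7.4%. Intervals would need to be 7–10% wider to match the t reference. These figures rest on the null rates, ICC scale, patient variance and absence of covariates stated in the working. For the linear secondary outcomes the same reasoning applies, but the size was not computed.

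This is a cheap improvement: more than a missing detail, because it affects the error rate of the primary test, but not evidence that the trial's test will in fact run at 7–9%. A reader might also blame the t reference for power below 80% at 10:5. Most of that gap comes from the layout, which already gives only 74–76% with z. The differing practice counts (15, 17 or 20) are a separate matter to reconcile.

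**What to change.** In sections 6, 6.1 and 6.2:

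1. Name the estimator.
2. State that the whole-period, 6-month and 12-month group effects are tested against a t distribution with practice-based degrees of freedom (Satterthwaite, or practices minus the number of practice-level parameters), with confidence intervals from the same reference. Only the second option, as practices minus 2, was simulated here. If cooperative or practice SES enters the model, its parameters come off the count.
3. Leave the pure time-by-group interaction on its usual within-patient reference.
4. State which practices are analysed, since the degrees of freedom depend on it.

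Optionally, add a permutation check of the primary p-value. It must respect the stratification by cooperative and SES and, if EMBOSS controls are pooled, the two linked randomisations, so it takes more work than a software option.

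The cost is a few sentences, a software setting (the team should confirm that its software offers the chosen method for logistic models), intervals 7–10% wider than with 1.96, and about 3–7 points of power. At 10:5, power is about 67–70% with t against 74–76% with z.
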